5.3 LIFESTYLE CONSIDERATIONS

Participants will be asked to:

- Finish the dinner (provided) by 5 pm on day 1, followed by an approximate 15-hour water-only fast;
- Self-monitor blood glucose on day 1 (morning before breakfast) and on day 2;
- Self-monitor blood ketone (BHB) on day 1 (morning before breakfast) and on day 2.

5.4 SCREEN FAILURES

Screen failures are defined as participants who consent to participate in the trial but are not subsequently randomly assigned to the study intervention or entered in the study.

A minimal set of screen failure information including demography, screen failure details, eligibility criteria will be retained to ensure transparent reporting of screen failure participants, to meet the Consolidated Standards of Reporting Trials (CONSORT) publishing requirements and to respond to queries from regulatory authorities.

5.5 STRATEGIES FOR RECRUITMENT AND RETENTION

Potential participants will be recruited via telephone and email.
Participants will be enrolled via Zoom teleconference (<https://www.zoom.com>).

6 STUDY INTERVENTION

6.1 STUDY INTERVENTION(S) ADMINISTRATION

6.1.1 STUDY INTERVENTION DESCRIPTION

Participants will be asked to consume a ready-to-eat dinner before 5 pm on day 1.

Participants will be asked to refrain from consuming any food or drinks (except water) for 15 hours.

On day 2, subjects will be asked

- to continue the water-only fast for 4 more hours (Water Fast Group);
- to consume a breakfast, and then continue to water-only fast for 4 more hours (Breakfast Group);
- to consume a Fast Bar™, and then continue to water-only fast for 4 more hours (Fast Bar Group).

6.1.2 DOSING AND ADMINISTRATION

Participants will undergo 15 to 19 hours of water-only overnight fasting.

Participants will consume a breakfast or a Fast Bar™.

6.2 PREPARATION/HANDLING/STORAGE/ACCOUNTABILITY

6.2.1 ACQUISITION AND ACCOUNTABILITY

This study will use food products developed by the L-Nutra company.

Study coordinator will be responsible to keep the inventory of products.

Prepared study kits that includes all necessary study materials will be mailed to participants once they are enrolled and consented.

6.2.2 FORMULATION, APPEARANCE, PACKAGING, AND LABELING

L-Nutra company handles the formulation, appearance, packaging and labeling of all the food products for this study.

The custom ready-to-eat dinner prior to fasting will be provided by Nutrition For Longevity, a subsidiary of L-Nutra.

Dinner meal ingredients: Sockeye Salmon, Organic Red Cabbage, Organic Cooked White Rice, Organic Stir Fry Greens, Organic Broccoli, Organic Cauliflower Rice, Organic Carrots, Organic Onion, N4L Imported EVOO, N4L Teriyaki Sauce (Organic Pineapple Juice, Organic Japanese Rice Wine, Organic Ginger Root, Organic Tamari), Organic Garlic, Organic Scallions.

Contains Fish, Soy, Tree Nuts.

The breakfast bar is formulated to mimic a typical breakfast in energy contents.

Breakfast ingredients: Tapioca Syrup, Dates, Almond Butter, Almonds, Soy Protein Crisps (Soy Protein Isolate, Rice Flour, Malt Extract (may contain wheat), Micellar Casein, Whey Protein Concentrate, Pea Protein, Flaxseed, Almond Protein, Maltodextrin, Sunflower Lecithin, Sea Salt, Natural Flavor. Contains Milk, Soy and Almonds. May contain Wheat.

Fast Bar™ ingredients: Macadamia Nuts, Pecan Pieces, Inulin, Almond Meal, Almond Butter, Honey, Coconut Flour, Flaxseed Meal, Vanilla Powder, Sea Salt, Rosemary oleoresin.

Product Contains: Tree nuts (almonds, coconut, macadamia nuts, pecans). Manufactured on equipment that also processes other tree nuts, peanuts, soy, wheat, egg, and milk.

6.2.3 PRODUCT STORAGE AND STABILITY

Food items need to be stored in a cool, dry place.

6.2.4 PREPARATION

N/A

6.3 MEASURES TO MINIMIZE BIAS: RANDOMIZATION AND BLINDING

After screening, participants will be block randomized (12 blocks of 9 each) in a 1:1:1 allocation to the breakfast, Fast Bar and water-only fast groups using a predetermined randomization table.

The following measures will be performed to minimize biases:

- Subjects will be randomly assigned to either one of the two arms of the study;
- Data and/or specimens will be labeled with a code that the research team can link to personal identifying information;
- The study foods will be labelled with the participants' code (by research personnel not directly interacting with the participants).

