1.2 SCHEMA

1.3 SCHEDULE OF ACTIVITIES (SOA)

	Screening	Day 1	Day 2				
Day		1	T0	T1	T2	T3	T4
Hours			Baseline	+1 h	+2 h	+3 h	+4 h
Example clock times			8 am	9 am	10 am	11 am	12 pm
Procedures							
Informed consent	X						
Randomization	X (1)						
Blood draw (Fingerstick)		X (morning, fasting)	X	X	X	X	X
• ketone (BHB)							
• glucose							
Intervention							
Healthy Eating Style	X (2)						
Dinner, followed by 15 h water-only fasting		X (before 5 pm)					
Breakfast Bar			X (after T0 test)				
Fast Bar™			X (after T0 test)				
Water-only fast			X	X	X	X	X
Questionnaires/ Surveys							
Demographics	X						
Contact Information	X						
Medical history							
Concomitant medications	X						
24-h dietary recall	X						
Food diary		X					
Self-evaluation			X (after T0 test)				X
Food evaluation				X			

(1) Subjects will be assigned to study arms according to the randomization scheme generated by using the web site Randomization.com (<http://www.randomization.com>).

(2) Subjects will be provided with a USDA MyPlate Plan according to his/her BMI and physical activity level (<https://www.choosemyplate.gov/resources/MyPlatePlan>) and encouraged to adopt the recommended healthy eating style for 2-3 days before starting the trial.

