5.2 EXCLUSION CRITERIA

An individual of any race and ethnicity who meets any of the following criteria will be excluded from participation in this study:

- Has any medical disease or condition that, in the opinion of the principal investigator (PI) or appropriate study personnel, precludes study participation* (*Including acute, subacute, intermittent or chronic medical disease or condition that would place the subject at an unacceptable risk of injury, render the subject unable to meet the requirements of the protocol, or may interfere with the evaluation of responses or the subject's successful completion of this trial);
- History of gastric bypass (based on medical history provided at screening);
- Under medications aimed at keeping blood glucose under control (based on medical history provided at screening);
- Type 1 diabetes (based on medical history provided at screening);
- Taking insulin, insulin analogs, or octreotide (based on medical history provided at screening);
- Food allergies which would make the subject unable to consume the food provided (based on medical history and information provided at screening) (participants will be asked to review the ingredient lists for the dinner meal, the breakfast and the Fast Bar™, and to state that they are not allergic to the ingredients to the best of their knowledge);
- Women who are pregnant;
- Alcohol dependency (alcohol intake greater than two drinks per day for women and three drinks per day for men) (based on medical history and information provided at screening).

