6.4 STUDY INTERVENTION COMPLIANCE

Participants will be recruited via email and/or telephone.

Potential participants will be provided with study-related documents over the email or mail.

Potential participants will be consented over a Zoom conference with the study coordinator. A signed consent form will be emailed back to the PI using Docusign.

Participants will be monitored via Zoom teleconference by the study personnel.

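### Section 6.3 prints a fixed block size of 9, and one study coordinator both consents participants and keeps the product inventory, so nothing in the available text keeps the enrolling role from the running arm counts

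*Combined protocol and SAP*

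**What the plan says.** On the sequence, section 6.3 states that "participants will be block randomized (12 blocks of 9 each) in a 1:1:1 allocation", and that this is done "using a predetermined randomization table". A footnote to the Schedule of Activities (section 1.3) names the source of the list: "Subjects will be assigned to study arms according to the randomization scheme generated by using the web site Randomization.com".

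On roles, section 6.2.1 states: "Study coordinator will be responsible to keep the inventory of products". Section 6.4 states: "Potential participants will be consented over a Zoom conference with the study coordinator". Study kits "will be mailed to participants once they are enrolled and consented" (section 6.2.1), so product leaves stock while enrolment is still running.

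On safeguards, section 6.3 places randomization after screening. It also has the foods labelled with participant codes by staff who have no direct contact with participants. The available text does not say who holds the table, when a code is released, or whether the coordinator is blinded to arm. The design is called single-blinded without naming who is blinded.

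On discretion at entry, section 5.2 allows exclusion for a condition that, "in the opinion of the principal investigator (PI) or appropriate study personnel, precludes study participation".

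**The concern.** Randomization protects against selection bias only while the person who decides on entry cannot foresee the next arm. Here the block size is fixed and printed, so anyone with the protocol and the running arm totals can work out what remains in the current block. The three arms draw differently on stock: a Fast Bar, a breakfast bar, or no bar. A stock count by product therefore carries the arm totals, and coding the individual packages does not hide them.

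The role that keeps the stock also consents participants, and the entry criteria leave room for judgement. If foresight affected who was invited, scheduled or judged eligible, the arms would differ before treatment. The intention-to-treat analysis in section 9.3 would not repair that. The primary comparison of Fast Bar with breakfast bar is tested one-sided at 5% (section 9.4.1) with 36 per arm, so a modest induced difference in expected BHB would matter.

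**Working it through.** **Inputs.** Block size 9, 12 blocks, 1:1:1, hence 3 + 3 + 3 per block (section 6.3). Planned total 108 and 36 per group (section 9.2). One-sided 5% level (section 9.4.1). Assumed for the ceiling: the guesser knows the block size and all past allocations immediately.

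**1. The plan's own total.** Section 9.2 needs 32 per group for the Fisher test; with 10% loss, 32/0.9 = 35.6, rounded up to 36. Then 3 × 36 = 12 × 9 = 108, which matches. (Section 9.2 also gives 32 for the fasting group; 36 + 36 + 32 = 104 fits neither 108 nor 1:1:1. The block structure implies 36, which is used here.)

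**2. Allocations certain in advance, full and immediate knowledge.** An allocation is certain when only one arm has slots left.
- 9th position: always, probability 1.
- 8th: the last two slots are the same arm, 2/8 = 0.25.
- 7th: the last three slots are the same arm, (2/8) × (1/7) = 0.0357.
- Earlier positions: never.

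Sum = 1.286 per block, or 14.3%; × 12 = 15.4 of 108.

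**3. Allocations with at least one arm already ruled out.** By exact enumeration, the probabilities for positions 4 to 9 are 0.036, 0.143, 0.357, 0.679, 1 and 1. Sum = 3.214 per block, or 35.7%; × 12 = 38.6 of 108.

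**4. Best guess.** The guesser names the arm with most slots left. The chance of being right at each position is the expected value of (largest remaining count)/(slots remaining):

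| Position | 1 | 2 | 3 | 4 | 5 | 6 | 7 | 8 | 9 |
|---|---|---|---|---|---|---|---|---|---|
| P(correct) | 0.333 | 0.375 | 0.429 | 0.446 | 0.471 | 0.536 | 0.571 | 0.625 | 1.000 |

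Sum = 4.787 per block, or 53.2%; × 12 = 57.4 of 108. Chance gives 3 per block, or 36 of 108.

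**5. Effect of delay.** If knowledge runs one participant behind, position k is guessed from what was known at position k − 1.
- Certain allocations: 0.25 + 0.0357 = 0.286 per block; × 12 = 3.4 of 108.
- Best guess: 4.787 − 1.000 + 0.333 = 4.120 of 9, or 45.8%.
- Two behind: 0.036 certain per block. Three behind: none certain, best guess 39.9%. Five behind: 36.1%.

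**6. Mixed block sizes.** Take four blocks each of 6, 9 and 12, which total 4 × 27 = 108. For someone who knows each size and the running counts, the expected correct guesses are 4 × (3.367 + 4.787 + 6.144) = 57.2 of 108, and the certain allocations are 4 × (1.200 + 1.286 + 1.333) = 15.3. Both are almost unchanged from fixed blocks of 9. If the possible sizes are known but their order is not, simulation still puts the best guess near 53%, but certain allocations fall from 14.3% to about 2.6%. The fall is somewhat smaller if the number of blocks of each size is also known.

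**7. Illustration of the stake, with assumed steering.** Suppose full, immediate knowledge. Suppose also that expected BHB of those enrolled is raised by η SD whenever Fast Bar is behind breakfast bar in the running count, and lowered by η when it is ahead. In simulation the bias is about 0.73η. With noncentrality = bias × √(36/2) and 70 degrees of freedom:

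| η (SD) | Bias (SD) | One-sided 5% error becomes |
|---|---|---|
| 0.10 | 0.07 | about 9% |
| 0.25 | 0.18 | about 19% |
| 0.50 | 0.37 | about 46% |

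The documents give no basis for any value of η.

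**The case against.** The strongest reply is that the mechanism is inferred. Section 6.2.1 says only that the coordinator keeps the inventory. It does not say that stock is tracked kit by kit or by arm, that the coordinator packs or mails kits, or that the coordinator holds the list. Section 6.3 gives labelling to staff kept apart from participants. The contents list also shows a section on key roles and governance (10.1.5) that is not in the text available for review, and it may settle who does what. All of this stands. It limits the claim to what the plan leaves open.

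Second, steering needs prognostic information as well as foresight. Under the Schedule of Activities the first BHB reading is on Day 1, after randomization. Whoever judges eligibility has only indirect indicators such as BMI and the dietary recall. This also stands, and it makes the larger values of η in the illustration less plausible.

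Two stronger readings are tempting and are not supported:
- A reader might infer that the later allocations of each block can simply be predicted, and that enrolment can be steered. Even at the ceiling, only the 9th allocation is always certain; the 8th is certain in 25% of blocks and the 7th in 3.6%. Nothing in the documents shows that the coordinator has the knowledge required.
- A reader might infer that Day 2 teleconference monitoring ("Participants will be monitored via Zoom teleconference by the study personnel") reveals the sequence. Seeing who eats a bar and who does not leaves the two bar arms interchangeable, so it cannot steer the primary comparison. It also comes late. At 108 participants in 3 months, about 1.2 a day, an assumed lag of 4 to 7 days puts 5 to 8 later participants already in the sequence; at five the best guess is 36%, close to chance.

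**Conclusion.** The concern holds as a weakness in stated design choices, not as a demonstrated leak. A fixed, published block size and a coordinator who both consents and keeps stock make prediction possible, and nothing available for review closes that route. The ceiling is 1.29 of 9 allocations certain (about 15 of 108) and 53% correct guesses against 33%. It rests on complete and immediate knowledge of past allocations. With a lag of one participant it is 0.29 of 9 certain (about 3 of 108) and 46% correct. The real figure depends on how stock is recorded and who sees the record, which the available text does not say. The plan should be changed before enrolment because the change is cheap, not because bias has been shown.

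**What to change.** **Main change (sections 6.2.1 and 6.3).** Assign inventory by product or arm, and custody of the randomization table, to the staff already named in section 6.3 who have no direct contact with participants. The coordinator keeps consent and participant contact without access to arm-level stock. State that each code is released only after consent is signed and eligibility is recorded as final. If section 10.1.5 assigns these duties, bring it into line.

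**Supporting change (section 6.3).** Replace the 12 blocks of 9 with randomly ordered blocks of mixed size totalling 108 at 1:1:1. Keep the sizes out of the protocol and withhold them from anyone who screens or consents. This mainly removes certainty at block ends. It does not by itself lower the average guess rate for someone who knows the possible sizes and the running counts, so it does not replace the main change.

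**Cost.** A regenerated list before first enrolment and one duty moved between existing staff. The total stays at 108. The arms may be slightly unequal if enrolment stops inside a block.

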6.4 STUDY INTERVENTION COMPLIANCE

Participants will be recruited via email and/or telephone.

Potential participants will be provided with study-related documents over the email or mail.

Potential participants will be consented over a Zoom conference with the study coordinator. A signed consent form will be emailed back to the PI using Docusign.

Participants will be monitored via Zoom teleconference by the study personnel.

6.5 CONCOMITANT THERAPY

N/A

6.5.1 RESCUE MEDICINE

N/A

7 STUDY INTERVENTION DISCONTINUATION AND PARTICIPANT DISCONTINUATION/WITHDRAWAL

7.1 DISCONTINUATION OF STUDY INTERVENTION

N/A

7.2 PARTICIPANT DISCONTINUATION/WITHDRAWAL FROM THE STUDY

Participants are free to withdraw from participation in the study at any time upon request.

An investigator may discontinue or withdraw a participant from the study for the following reasons:

- Significant study intervention non-compliance;
- If any clinical adverse event (AE), biomarker abnormality, or other medical condition or situation occurs such that continued participation in the study would not be in the best interest of the participant;

In case of discontinuation/withdrawal, the data collected up to the time of discontinuation from that specific participant will still be used as part of the trial database and statistical analysis of trial outcome.

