9.3 POPULATIONS FOR ANALYSES

All participants will be included in the intention-to-treat analyses of the results. Participants who are removed from study for non-compliance or for safety reasons will still have their data included in the final analysis, unless they withdraw consent to have their data included, and will not be replaced.

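### Section 7.2 permits withdrawal from the study for non-compliance and provides only for data up to that point, so the T3 and 0-4 h BHB readings needed for the intention-to-treat analysis in 9.3 are not secured

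*Combined protocol and SAP*

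**What the plan says.** Section 7.2 begins its list of grounds with "An investigator may discontinue or withdraw a participant from the study for the following reasons". There are two grounds.

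- The first is "Significant study intervention non-compliance", with no definition of significant.
- The second opens "If any clinical adverse event (AE), biomarker abnormality, or other medical condition or situation occurs" and carries a condition: "such that continued participation in the study would not be in the best interest of the participant".

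On data, 7.2 says that "the data collected up to the time of discontinuation from that specific participant will still be used as part of the trial database" and the statistical analysis. It does not mention readings after that time.

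The section headed "7.1 DISCONTINUATION OF STUDY INTERVENTION" contains only N/A, as does 7.3 on loss to follow-up. No section describes a participant who is off the intervention but still taking fingersticks.

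Section 9.3 says "All participants will be included in the intention-to-treat analyses of the results" and adds: "Participants who are removed from study for non-compliance or for safety reasons will still have their data included in the final analysis". The exception is withdrawal of consent for data use, and those removed are not replaced.

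Sections 9.1 and 9.4.2 define the primary outcome as BHB at T3 together with the change in BHB AUC from 0 to 4 hours. The Schedule of Activities (1.3) places randomisation at screening and the fingersticks at T0 to T4 on day 2.

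**The concern.** An intention-to-treat comparison needs the outcome to be sought from everyone randomised, whether or not they followed the assigned regimen. Section 7.2 joins two separate events, departing from the regimen and leaving the study, and makes no provision for readings after the second. Section 9.3 can then include only what was measured before removal. For the primary outcome that may be nothing usable.

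The loss need not be random. Non-compliance here largely means eating during a fast or not eating the assigned bar. Section 4.3 itself says that food may markedly affect ketogenesis, so the behaviour that can lead to removal also acts on the endpoint. A comparison restricted to those with readings could then differ from the comparison of the arms as randomised. The test is one-sided (9.4.1), and losing off-plan eaters from the Fast Bar arm would move the estimate in the hypothesised direction.

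**Working it through.** **1. The plan's own figures.** Section 9.2 assumes BHB of 0.25 (SD 0.19) mM for Fast Bar and 0.16 (SD 0.05) mM for breakfast, one-sided alpha 0.05 and 80% power.

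- Pooled SD = sqrt((0.19² + 0.05²)/2) = sqrt(0.0193) = 0.1389, so d = 0.09/0.1389 = 0.648. The noncentral t gives 31 per group with power 0.8097, as stated.
- Fisher's exact test for 67% vs 33%, one-sided, gives 32 per group with power 0.8164, as stated.
- Allowing for 10% loss: 32/0.9 = 35.6, so 36 per group, as stated.

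**2. Power under loss.** With 10% lost, 36 x 0.9 = 32.4, so 32 per group remain. Power is 0.821 (t test) and 0.816 (Fisher). The planned loss does not take power below 80%. What remains is possible bias, which the 10% allowance does not address.

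**3. What removal costs, by time of removal, if readings stop at removal.**

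- During the roughly 15-hour overnight fast, after randomisation: all day 2 readings, hence both T3 and the AUC.
- After T0 and before T3: the T3 value and a complete AUC.
- After T3 and before T4: a complete AUC only.
- After T4: nothing.

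The exposed period therefore runs from the start of the overnight fast, not only through the four hours after the bar.

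**4. Illustration of size.** The documents give no removal rate, so the following are assumptions: a share f of the Fast Bar arm eats off-plan, would have had the breakfast mean of 0.16 mM, and is removed before T3, with no such removals in the breakfast arm.

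- Mean if everyone is measured: (1 - f) x 0.25 + f x 0.16.
- f = 10%: 0.225 + 0.016 = 0.241. The difference is 0.241 - 0.16 = 0.081. Without these participants it is 0.090, and 0.090/0.081 = 1.11, an excess of 0.009 mM or about 11%.
- f = 5%: 0.2375 + 0.008 = 0.2455. The difference is 0.0855, and 0.090/0.0855 = 1.05, an excess of 0.0045 mM or about 5%.

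**5. Wider range.** If the removed share f would have differed from that arm's completers by g, the completers' mean is off by f x g. For f = 3-10% and g = 0.05-0.19 mM (also assumptions) this is 0.03 x 0.05 = 0.0015 to 0.10 x 0.19 = 0.019 mM, or 2-21% of 0.09 mM.

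**6. Against sampling error.** The standard error of the difference at 36 per group is sqrt((0.19² + 0.05²)/36) = 0.033 mM. An excess of 0.009 mM is about 0.27 of a standard error.

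**7. Direction.** With removals in both arms, the error is the Fast Bar f x g minus the breakfast f x g. Off-plan eaters removed from the breakfast arm would partly offset the excess. The documents do not fix the net direction.

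**The case against.** The strongest reply is that 7.2 is permissive and consistent with 9.3: data in hand are kept and analysed, removed participants are not replaced, and 9.2 already allows for about 10% loss. With a single eating occasion and four hours of readings, there is little intervention left to stop, which makes N/A in 7.1 understandable. Much of this stands. There is no outright contradiction, and power is covered.

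A reader might infer more than the documents support:

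- **That readings after removal are never taken and the intention-to-treat analysis is impossible.** The rule says may, and nothing forbids later readings. An analysis using partial data is possible with a stated missing-data method.
- **That an abnormal BHB or glucose value alone leads to removal.** The best-interest condition applies, which makes this a participant-safety clause. Section 9 also defines the primary outcome by BHB only, although the synopsis and section 3 list glucose as well.
- **That staff knowledge of arm drives removal in the primary contrast.** The water-only arm is evident to anyone monitoring, but it lies outside the Fast Bar vs breakfast comparison. For the two bars, 6.3 has foods coded by personnel who do not interact directly with participants.

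The objection does not remove the gap. Retaining data in hand does not supply a T3 value that was not taken. Because randomisation precedes the overnight fast, the window is also longer than four hours.

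**Conclusion.** The concern holds as a gap in data collection. Under the stated rule, a participant removed for non-compliance before T3 or T4 need not have the readings that the primary outcome requires, and such loss can be related to BHB. The analysis promised in 9.3 is put at risk but not ruled out.

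The size is unknown. The excess of about 5-11% (0.0045-0.009 mM) rests on assumed removal of 5-10% in the Fast Bar arm only, on those participants falling to the breakfast mean, and on their later readings not being taken. It is small beside the sampling error, and removals in the breakfast arm could reduce it. The case for a change rests on how easily the loss can be avoided, not on a demonstrated large bias.

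**What to change.** Reconcile 7.1, 7.2 and 9.3, and add a data-collection rule with these elements:

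- Non-compliance alone does not end data collection.
- The remaining scheduled T1-T4 fingersticks are still requested, unless the participant withdraws or the investigator judges it unsafe.
- The time and reason of each deviation are recorded.
- The readings are analysed in the assigned arm.

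Criteria for stopping the fast or for withdrawing a participant for safety remain the sponsor's to set; nothing here proposes one. Values that are still missing will need a stated method, which 9.4 does not give and which this rule does not supply.

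The cost is a short amendment. The readings are already in the schedule, and 6.2.1 has the study materials mailed to participants in advance. The small downside is that off-plan readings enter the primary comparison and may slightly reduce the observed difference.
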